7.3 Missing data

The occurrence of missing data in this trial is expected to be low and equally distributed across the treatment groups. We estimate that careful selection of patients during the screening phase and the consent process should result in no more than 10% missing data from patients who drop out before completing the 72 week treatment period. In primary, intention-to-treat analyses, subjects with missing data will be considered unimproved on the primary outcome measure.

The proportions with missing data will be compared across treatment groups using χ^2 tests. If the amount of missing data exceeds 10%, then a variety of sensitivity analyses will be carried out to compare to the primary analysis using all available non-missing data:

- (1) compare pessimistic and optimistic imputations of the missing values,

- (2) correct for missing data using multiple imputation with 10 replicated samples, and
- (3) use mixed random effects logistic or linear regression models, depending on the type of outcome measure.

Sensitivity analyses (2) and (3) assume that the missing data are missing at random (MAR). It is possible that the missing data is not MAR and, therefore, non-ignorable. A few statistical methods are available when there are non-ignorable missing data patterns and these may be employed to assess sensitivity of the results to non-ignorable missing data if the level on the missing data exceeds 10%; however all such methods involve strong assumptions that cannot be verified from the available data.

7.4 Justification of sample size

A total of 280 patients in 2 groups of equal size (140 per group) will be included to compare the efficacy of obeticholic acid group vs. placebo group with the primary outcome measure of histological improvement in NAS (as defined in sections 3.4 and 6.1). A sample size of 280 patients with 1:1 randomization would provide 90% power to the study hypothesis to detect a significant difference between the two groups with a type I error rate of 0.05. This sample size takes into account that 10% of participants will not have 72 week biopsies and will be considered not improved based upon intention to treat analysis. The sample size estimation is based upon the assumption that the minimum clinically important difference, defined as 50% higher relative rate of improvement in the obeticholic acid group vs. the placebo group, will be expected with the assumed response rates in the placebo group in the placebo group of 39% (based on PIVENS data and 2 to 1 split for patients on vs not on vitamin E at start of trial) versus expected percent with improved NAFLD in the obeticholic acid group to be 58%. This estimate was derived using centrally-read histology data from the PIVENS trial in which 48% of the vitamin E-assigned group and 20% of the placebo-assigned group had the primary outcome similar to that defined for the FLINT trial. Weighting these data by the FLINT investigator's estimate that 2/3 of patients enrolled in the FLINT trial will be taking vitamin E, gives the 39% response rate. These sample size estimations are conservative and would have a minimal likelihood of a type 2 error.

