A formal vanguard analysis, marking the end of the vanguard phase of the FLINT trial, will be performed approximately 65 weeks after the first patient is randomized. The analysis will be focused on interim efficacy outcomes and safety information using data from the estimated 25-40% of patients who will have completed at least 24 weeks of follow-up by the time of the interim analysis. Our pre-specified interim criterion for efficacy for continuing the FLINT trial beyond the vanguard phase is based on serum ALT: the criterion for continuation will be considered met if the upper 95% confidence limit on the between-group mean difference in mean changes from baseline to the 24 week measure of ALT, comparing the obeticholic acid versus placebo groups, is at least a 20% net reduction in serum ALT from the overall baseline mean ALT. The analysis will also include detailed safety data, as required by the DSMB, to determine whether any emergent safety issues are present. This vanguard safety analysis will consist of, but is not limited to, counts of adverse events (AEs) and serious adverse events (SAEs) by treatment group with associated P-values based on Fisher's exact tests or other tests, as appropriate. The final decision as to whether to continue the FLINT trial beyond the vanguard phase will be made by the NIDDK program official for the NASH CRN trial, which will be informed by any recommendations from the FLINT DSMB, taking the interim criterion for efficacy, safety, and other relevant information that may arise into account.

Interim analysis

The DSMB will review one planned interim analysis of the primary histological outcome measure. O'Brien-Fleming statistical stopping guidelines for efficacy will be applied. This interim efficacy analysis will occur when approximately 50% (140 of the 280 patients) have completed both baseline and 72 week biopsies. Based on the Lan-DeMets method for group sequential trials using O'Brien-Fleming boundaries (Reboussin et al., 2000), the levels of significance for the interim and final analyses will be $\alpha=0.00305$ and $\alpha=0.049$, respectively.

Sample size considerations

- Total of 280 patients in 2 groups of equal size (140 per group)
- Primary comparison: Obeticholic acid group vs. Placebo group
- Primary outcome measure: Histological improvement in NAFLD (defined above)
- Error protection: Type I = 0.05 and Type II = 0.10 (90% power)

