- Missing data: 10% will not have 72 week biopsies and will be considered not improved
- Minimum clinically important difference:
 - 50% higher relative rate of improvement in the obeticholic acid group vs. the placebo group
- Assumed response rates:
 - Expected percent with improved NAFLD (defined above) in the placebo group: 39% (based on PIVENS data and 2 to 1 split for patients on vs not on vitamin E at start of trial)
 - Expected percent with improved NAFLD in the obeticholic acid group: 58%

Safety monitoring: NIDDK appointed DSMB will monitor the data for safety and efficacy for outcomes such as hepatotoxicity, pregnancy, and any other outcomes or events identified as safety-related.

1. Hypothesis and principal objective

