7.2 Statistical analysis

Primary hypothesis

Statistical analyses for the primary hypothesis will follow the intention-to-treat paradigm, which means that all randomized patients with baseline and 72 week liver biopsies will be included in the treatment group to which they were assigned. Any randomized patient who does not have the requisite biopsies will be accounted for and compared by assigned treatment group. Patients not able to be included in the intention-to-treat analyses will be compared to those who are included with respect to demographic and other characteristics.

Since the primary outcome measure, defined in sections 3.4 and 6.1, is a binary indicator of improvement in histologic activity score after 72 weeks of treatment compared to baseline and since the randomization is stratified by clinic and diabetes status, P-values will be derived from the Mantel-Haenszel χ^2 test for stratified 2x2 tables. The proportion of patients improved in the group assigned to obeticholic acid will be compared to the group assigned to placebo and a two-tailed p-value of ≤ 0.05 will be considered statistically significant.

Stratification

Given the randomized design and adequate size planned for the FLINT trial, it is unlikely that confounding of the treatment groups by covariates related to the change in histologic activity score will occur. However, if confounding should occur, multivariate-adjusted logistic regression analyses with histologic improvement as the binary response and treatment group indicator and any suspected confounders as covariates will be carried out to determine the sensitivity of the primary P-value to confounding.

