7.6 Interim analysis

The DSMB will review one planned interim analysis of the primary histological outcome measure. O'Brien-Fleming statistical stopping guidelines for efficacy will be applied. This interim efficacy analysis will occur when approximately 50% (140 of the 280 patients) have completed both baseline and 72 week biopsies. Based on the Lan-DeMets method for group sequential trials using O'Brien-Fleming boundaries,⁹⁶ the levels of significance for the interim and final analyses will be $\alpha=0.00305$ and $\alpha=0.049$, respectively.

Adverse events and other safety measures

The interim analysis will also include detailed safety data, as required by the NIDDK and DSMB, to determine whether any emergent safety issues are present. This interim safety analysis will consist of, but is not limited to, counts of adverse events (AEs) and serious adverse events (SAEs) by treatment group with associated P-values based on Fisher's exact tests or other tests, as appropriate. The final decision as to whether to continue the FLINT trial beyond the vanguard phase will be made by the NIDDK program official for the NASH CRN trial, which will be informed by any recommendations from the FLINT DSMB, taking the interim criterion for efficacy, safety, and other relevant information that may arise into account.

An ongoing assessment of adverse events and other safety measures by the Data and Safety Monitoring Board will determine whether the trial should be continued throughout the duration of the trial including at the interim vanguard analysis time point.

Other interim analyses

An independent Data and Safety Monitoring Board (DSMB), appointed by the NIDDK, will review the protocol for the FLINT trial and monitor the accumulated vanguard, interim, and safety data as the trial progresses to ensure patient safety and to review efficacy. The DSMB is a multidisciplinary group with a written charge provided by the NIDDK. The DSMB reports to the NIDDK, which will in turn, communicate DSMB recommendations to the investigators, as appropriate. The DSMB will hold a meeting to approve the protocol. After the trial commences, the DSMB will meet twice a year to review data and other issues. The DSMB may conduct more frequent meetings if necessary to fulfill its charge. It may also request additional safety reports on a more frequent basis. For example, all serious adverse events are reported to the DSMB for their consideration and recommendations as they occur.

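### Section 7.4 claims 90% power after allowing for 10% missing biopsies, but no step of the calculation contains that allowance; power is about 83% if 39% and 58% are rates among biopsied patients

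*Protocol*

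**What the plan says.** Protocol section 7.4 sets the size: "A total of 280 patients in 2 groups of equal size (140 per group) will be included". It then states: "A sample size of 280 patients with 1:1 randomization would provide 90% power", at a type I error of 0.05. The synopsis, under Sample size considerations, repeats the error rates: "Error protection: Type I = 0.05 and Type II = 0.10 (90% power").

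The assumed rates of improvement are 39% on placebo and 58% on obeticholic acid. The target is a 50% higher relative rate. The synopsis gives the source of the placebo rate as "based on PIVENS data and 2 to 1 split for patients on vs not on vitamin E at start of trial". Section 7.4 supplies the components: 48% of the vitamin E-assigned group and 20% of the placebo-assigned group in the prior trial, weighted by an investigator estimate that two thirds of patients will take vitamin E.

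On missing biopsies, section 7.4 says: "This sample size takes into account that 10% of participants will not have 72 week biopsies and will be considered not improved". Section 7.3 applies the same rule in the primary analysis and expects no more than 10% missing. Section 7.4 closes: "These sample size estimations are conservative and would have a minimal likelihood of a type 2 error".

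Section 7.2 fixes the test as two-sided: "a two-tailed p-value of ≤ 0.05 will be considered statistically significant". Section 7.6 adds one interim look: "the levels of significance for the interim and final analyses will be $\alpha=0.00305$ and $\alpha=0.049$, respectively".

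**The concern.** An allowance for missing outcomes has to enter somewhere, either as lower response rates or as a larger sample. Here 140 per group is the size that 39% versus 58% needs before any allowance, and the shown derivation of the two rates removes nothing. The text therefore claims a protection that its arithmetic does not display.

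The type II error is at stake. Counting missing biopsies as not improved lowers both rates and shrinks the difference between them. If that dilution has not yet been applied, the risk of missing the target effect is about 17%, not the stated 10%. The closing sentence of 7.4 adds to the problem, because it tells the reader that the estimate errs on the safe side and shows nothing to support this.

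**Working it through.** **Inputs.** 140 per group, 1:1, 90% power, 39% versus 58%, 10% missing counted as not improved (synopsis; 7.4). Two-sided 0.05 (7.2). Final alpha 0.049 (7.6).

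**1. Source of the rates.** 2/3 × 48% + 1/3 × 20% = 32.0% + 6.7% = 38.7%, rounded to 39%. Then 1.5 × 38.67% = 58.0%. Neither step involves the 10%.

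**2. The plan's own figure.** With unpooled variance,

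n = (1.960 + 1.282)² × (0.39 × 0.61 + 0.58 × 0.42) / 0.19² = 10.507 × 0.4815 / 0.0361 = 140.1 per group.

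Power at 140 per group: SE = √(0.4815/140) = 0.0586; 0.19/0.0586 = 3.24; Φ(3.24 − 1.96) = 90.0%. The pooled formula gives 89.3% (144 per group for 90%), and exact enumeration of the Pearson test gives 89.0%. So the stated 280 and 90% reproduce with no step for missing biopsies.

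**3. Rates among biopsied patients, with the protocol's missing-data rule applied.** 0.9 × 39% = 35.1% and 0.9 × 58% = 52.2%, a difference of 17.1 points.

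SE = √[(0.351 × 0.649 + 0.522 × 0.478)/140] = √(0.4773/140) = 0.0584; 0.171/0.0584 = 2.93; Φ(2.93 − 1.96) = 83.4%.

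| Variant at 140 per group | Power |
|---|---|
| Unpooled | 83.4% |
| Pooled | 82.6% |
| Exact Pearson | 82.1% |
| Pooled, alpha 0.049 | 82.4% |
| Unrounded 38.7% v 58%, pooled / unpooled | 83.9% / 84.7% |

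For comparison, 90% power would need 172 per group (unpooled) or 175 (pooled).

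**4. Other routes to 140 with an allowance.** Inflating 144 by 1/(1 − 0.10) gives 160 per group. A continuity correction gives 154 undiluted and 187 diluted. Analysing only biopsied patients (126 per group) gives 86% (pooled) to 87% (unpooled). A one-sided 0.05 test on the diluted rates comes close (143 per group), but 7.2 fixes a two-sided test.

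**5. Rates already net of missing biopsies.** The implied rates among biopsied patients are 39%/0.9 = 43% and 58%/0.9 = 64%. Step 2 then applies directly and 90% stands.

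**6. Dependence on the placebo rate.** The target is relative, so a lower placebo rate gives a smaller absolute difference. Power at 140 per group, pooled, with no missing data:

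| Placebo | Obeticholic acid (× 1.5) | Power |
|---|---|---|
| 30% | 45% | 74% |
| 25% | 37.5% | 62% |
| 20% | 30% | 49% |

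**The case against.** The strongest defence is that the prior-trial figures are given as shares of assigned groups. That is natural wording for intention-to-treat rates in which missing biopsies already count as failures. On that reading 39% and 58% are net, 140 per group at 90% is right, and reproducing 140 without an allowance is what one should expect. This stands as a possible reading. Section 7.4 does not confirm it, and gives no missing-biopsy rate for the prior trial.

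Three stronger conclusions are tempting and are not supported.

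- **That power is 83% without condition.** This needs the rates to be among biopsied patients, which the protocol does not say. It also takes the full 10%, where 7.3 expects at most 10%; at 5% missing, power is 86% to 87%.
- **That the word conservative is the opposite of the truth.** This requires either the unproven reading or a lower placebo rate with the relative gain held at 50%. If the 19-point difference were held instead, power would rise as the placebo rate falls: about 91% at 30%, 92-93% at 25% and 94-95% at 20%. The 49% figure also supposes essentially no vitamin E-type response, against the investigators' two-thirds estimate.
- **That the 48% is applied to patients already on vitamin E at the qualifying biopsy.** The synopsis speaks of the start of the trial, 7.4 of patients who will be taking it, and 5.2 allows it to be started. Use at the time of the biopsy is not stated.

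**Conclusion.** The point holds in conditional form. The protocol states an allowance for 10% missing biopsies that appears in no step of its calculation: the size is the undiluted one, and nothing was taken off the rates.

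- If 39% and 58% are rates among biopsied patients, power is about 83% (84% to 85% with the unrounded 38.7%), and the type II error is about 17% instead of 10%. This assumes 10% missing in each group, all counted as not improved, and a two-sided 0.05 test. The final alpha of 0.049 costs about 0.2 points.
- If they already count missing biopsies as failures, 90% stands, and the 10% describes what the rates contain; it is not a further allowance.

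The documents do not decide between the two. On either reading, the closing claim of 7.4 is unsupported. The protocol's own type II error is 10% at best, which is not minimal. Because the target is defined as a relative gain, a high placebo rate is the favourable case, and the 39% depends on an estimate of vitamin E use.

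**What to change.** In section 7.4 and in the synopsis:

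1. State whether 39% and 58% are rates among biopsied patients or already count missing biopsies as not improved.
2. If they are among biopsied patients, restate power at 280 as about 83% with 10% missing. If they are net, say so and give the implied rates among biopsied patients, about 43% and 64%.
3. On either reading, delete the closing sentence of 7.4 on conservatism and type II error.
4. Add power for the 50% relative gain at lower placebo rates: about 74% at 30%, 62% at 25% and 49% at 20%, labelled as assuming no missing data.

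The cost is wording only. On the first reading the stated power becomes less favourable. No added patients are needed, and the design and primary analysis do not change.

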7.5 Vanguard analysis

An unmasked vanguard analysis, using change in ALT (U/L) from baseline to the 24 week follow-up visit as the primary vanguard outcome, will be carried out for review by the DSMB in order to advise the NIDDK on whether the FLINT trial should continue. The vanguard design requires that the vanguard analysis and the decision to continue must be completed before any patient undergoes a 72 week end-of-study biopsy. This means that the vanguard analysis of ALT change must occur approximately 65 weeks after the first randomized patient is enrolled when between 70 (25% of total sample size) and 112 (40%) will have a 24 week ALT measure, but before the first patient (or any other patient) has undergone a 72 week liver biopsy.

The vanguard analysis statistical guideline indicating sufficient evidence that, compared to placebo, 24 weeks of treatment with obeticholic acid results in a greater reduction in ALT (BL – 24 weeks) will be considered met if the upper 95% confidence limit for the net percentage reduction in mean ALT (BL-24 weeks) in the obeticholic acid group vs. placebo group is greater than or equal to 20%. The net reduction and 95% upper confidence interval will be calculated from a multiple linear regression model with patient level changes in ALT (U/L) at baseline minus ALT (U/L) at 24 weeks as the response variable (y) and independent variables: obeticholic acid indicator ($x_1=1$, if obeticholic acid, 0, if placebo) and baseline ALT (U/L) (x_2): $E(y_i)=\beta_0+ \beta_1x_1+ \beta_2x_2+\epsilon_i$, $i=1,2,\dots,n$; n =number of patients in the vanguard analysis and ϵ_i are i.i.d. Gaussian($0,\sigma^2$).

The estimated between group (obeticholic acid vs. placebo) difference in mean change in ALT from BL

to 24 weeks is b_2 with 95% CI: $b_2 \pm t_{n-3} \widehat{\sigma}(b_2)$ where t_{n-3} is the 97.5th percentile of the t-distribution with $n-3$ degrees of freedom and $\widehat{\sigma}(b_2)$ is the estimated standard error of b_2 from the regression analysis. The estimated net reduction in ALT in the obeticholic acid group, expressed as percentage of the overall baseline mean ALT, \overline{ALT} , is $100 \times b_2 / \overline{ALT}$ with upper 95% confidence limit: $100 \times [b_2 + t_{n-3} \widehat{\sigma}(b_2)] / \overline{ALT}$. SAS PROC REG will be used to fit the regression model and calculate the upper 95% confidence limit to determine whether its value is a 20% or more net reduction in ALT.

The vanguard analysis will also include detailed safety data DSMB, to determine whether any emergent safety issues are present. This vanguard safety analysis will consist of, but is not limited to, counts of adverse events (AEs) and serious adverse events (SAEs) by treatment group with associated P-values based on Fisher's exact tests or other tests, as appropriate.

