2.7 The vanguard study design

Because the data supporting obeticholic acid as a treatment of NASH is limited to one pilot clinical trial, animal studies, and cell culture studies, the FLINT trial of obeticholic acid to treat NASH will use a “vanguard” trial design. A vanguard trial is designed to analyze predetermined interim data and based on

this analysis, either continuation of recruitment and participation of subjects for the planned duration or discontinuation of the trial will occur. In the case of the FLINT trial, this study design will allow evaluation of an interim surrogate endpoint (serum ALT) to determine if sufficient evidence is found that obeticholic acid is having a beneficial effect to justify continuing enrollment and performing end-of-treatment liver biopsies.

One example of the vanguard trial design is the Action to Control Cardiovascular Risk in Diabetes (ACCORD) trial.⁷⁵ The ACCORD trial recruited subjects over two non-contiguous periods. An initial vanguard phase was conducted to test the trial design and feasibility. The focus was not on response variables, but the ability of interventions to control glycemic control and blood pressure to achieve these goals in an initial subgroup. The ACCORD trial was terminated early on the recommendation of the DSMB because of adverse outcomes associated with intense glycemic control, but these were not identified in the vanguard phase.

3. Study design

[figure not shown]

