3.3 Vanguard analysis

Rationale

In order to safeguard the interests of the patients against futility, unnecessary liver biopsies, and adverse events attributable to the study drug, the FLINT trial utilizes a vanguard study design. This is needed because there are no human data on the efficacy and safety of obeticholic acid as a treatment for NASH. The vanguard design is one that allows interim data analysis with a decision regarding trial design or continuation based on the results of this analysis.

Timing

The vanguard analysis will be performed 65 weeks after the enrollment of the first subject. We anticipate that approximately 25-40% of subjects will have completed 24 weeks of treatment with either placebo or obeticholic acid by this time.

Measures

ALT measurement at 24 week visit (window: 18-30 weeks after randomization).

Analysis

The interim ALT target will be considered met if the upper 95% confidence limit includes a 20% net reduction in serum ALT from baseline to 24 weeks comparing the obeticholic acid versus placebo groups.

Study continuation or discontinuation

After analysis of the interim vanguard data by the DCC, the results of the analysis will be presented and discussed during a meeting of the DSMB attended by the DSMB, DCC, and NIDDK. Shortly thereafter, the results of the analysis and the recommendations of the DSMB will be discussed on a conference call attended by the DCC, NIDDK staff, and industry partner. The final decision to continue or stop the study will be made by the NIDDK program official for the NASH CRN in consultation with the Data Coordinating Center, the DSMB, and the industry partner. This decision will be reached before any follow-up biopsies are obtained. The NASH CRN investigators will not be told the results of the analysis unless the decision has been made to discontinue the trial. If the NIDDK Program Official determines that the trial should be continued, only the decision to continue will be communicated; the investigators will not be told any details or results of the interim vanguard analysis. No study completion liver biopsies are to be performed until the decision has been made to continue the study.

Site notification of study termination

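### The vanguard ALT rule tests the favourable confidence limit, so meeting it shows only that a 20% net reduction is not excluded, yet the protocol calls this sufficient evidence of benefit

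*Protocol*

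**What the plan says.** Section 7.5 introduces the rule as "The vanguard analysis statistical guideline indicating sufficient evidence that, compared to placebo", 24 weeks of obeticholic acid gives a greater ALT reduction. The quantity it tests is this: "upper 95% confidence limit for the net percentage reduction in mean ALT (BL-24 weeks) in the obeticholic acid group vs. placebo group". A pass needs that quantity to be 20% or more. The response is each patient's baseline ALT minus week-24 ALT, so a positive value is a fall. The limit is the estimate plus t times its standard error, divided by the overall baseline mean ALT. The multiplier t "is the 97.5th percentile of the t-distribution with" n − 3 degrees of freedom.

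Section 2.7 gives the purpose of the interim look: "to determine if sufficient evidence is found that obeticholic acid is having a beneficial effect", enough to justify further enrolment and the end-of-treatment biopsies.

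Two other places word the criterion differently:

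- The synopsis, under Vanguard analysis, uses "the upper 95% confidence limit on the between-group mean difference in mean changes from baseline to the 24 week measure of ALT" and asks that it be at least a 20% net reduction. It states no sign.
- Section 3.3 says the target is met "if the upper 95% confidence limit includes a 20% net reduction in serum ALT".

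The regression in section 7.5 codes treatment as x_1 and baseline ALT as x_2, but takes the treatment difference and its interval from b_2.

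**The concern.** With a response in which positive means benefit, the upper limit is the best case the data allow. Asking the best case to reach 20% is a test of whether 20% can be ruled out. It is not a test of whether the drug does anything. For any true effect below 20%, fewer or noisier data make the rule easier to meet, which is the reverse of how an evidence rule behaves.

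This is the only efficacy criterion applied before end-of-treatment biopsies, which sections 3.3 and 5.8 hold back until the decision to continue. A monitoring board or program official told that the sufficient-evidence guideline was met could credit the result with more than it shows. The differing wordings add a second risk: two people working from different sections could apply different limits to the same data.

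**Working it through.** **Inputs.** Section 7.5 expects 70 to 112 patients with a week-24 ALT. These figures reproduce from the sample size: 0.25 × 280 = 70 and 0.40 × 280 = 112. Allocation is 1:1 (section 7.4). The threshold is 20% of mean ALT. The protocol states no ALT standard deviation and no pass probability. The residual SD is therefore my assumption, varied from 30% to 60% of baseline mean ALT.

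**Formulas**, all in percent of mean ALT, with b the estimated treatment difference and δ the true net reduction:

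- SE = 2 × SD / √n
- Section 7.5 rule: b + t × SE ≥ 20, so P(pass) ≈ Φ((δ + t × SE − 20) / SE)
- t = 1.996 for n = 70 (67 df) and 1.982 for n = 112 (109 df)

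**No true effect (δ = 0):**

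| n | SD | SE | t × SE | (t × SE − 20) / SE | P(pass) |
|---|---|---|---|---|---|
| 70 | 30 | 7.17 | 14.31 | −0.79 | 21% |
| 70 | 50 | 11.95 | 23.86 | 0.32 | 63% |
| 70 | 60 | 14.34 | 28.63 | 0.60 | 73% |
| 112 | 30 | 5.67 | 11.24 | −1.55 | 6% |
| 112 | 50 | 9.45 | 18.73 | −0.13 | 45% |
| 112 | 60 | 11.34 | 22.47 | 0.22 | 59% |

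A simulation that also estimates the residual variance agrees to within about one percentage point. The null pass rate reaches 50% when t × SE = 20, that is at SD = 20√n / (2t): about 42% for n = 70 and 53% for n = 112.

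**Results leaning the wrong way.** At n = 70 and SD 50%, the lowest passing estimate is 20 − 23.86 = −3.9%, which is ALT 3.9% higher on drug. A drug that truly raises ALT by 10% passes with probability Φ((−10 + 23.86 − 20) / 11.95) = Φ(−0.51), about 30%.

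**Comparators.** A rule requiring the lower limit to exceed zero passes an inactive drug 2.5% of the time by construction. At a true 20% reduction, the section 7.5 rule passes 97.5% of the time whatever the SD and n, because it then fails only when the t statistic falls below its 2.5th percentile.

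**The synopsis wording.** If change from baseline to week 24 is taken as week 24 minus baseline, benefit is negative and the upper limit is the least favourable end. The rule becomes b − t × SE ≥ 20. A true 20% reduction meets it 2.5% of the time. A true 30% reduction meets it with probability Φ((10 − t × SE) / SE): about 10% at n = 70 and SD 60%, and 41% at n = 112 and SD 30%.

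**The coefficient.** In the stated model the treatment effect is the coefficient of x_1, namely b_1. The quantity b_2 is the slope on baseline ALT. That slope has no units, so dividing it by a mean in U/L does not give a percentage reduction. Everything above uses the treatment coefficient.

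**The case against.** The strongest defence is that the favourable limit is a proper futility screen. Futility is a stated aim in section 3.3 and in the rationale for the 72-week duration in section 3.2, and a 97.5% pass rate at the target effect is what such a screen should deliver. The rule is also advisory. Section 7.5 calls it a guideline, and the synopsis and sections 3.3 and 7.6 leave the decision to the NIDDK program official, informed by the board, safety and other information. The board sees the unmasked analysis, so an estimate favouring placebo would be visible. A false pass does not alter the type I error of the histology test. All of this stands, and it lowers the severity. It does not make the evidence label correct.

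A reader might infer that the synopsis contradicts section 7.5 by setting the opposite, almost unattainable rule. The documents do not establish that. The synopsis states no sign, and section 7.5 itself describes its baseline-minus-week-24 quantity as a change from baseline to 24 weeks. The wording in section 3.3 is also compatible with the favourable limit. The opposite rule is a possible reading only, and its very low pass rate applies near a true 20% effect, not to larger ones.

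A reader might also infer that an inactive drug passes about as often as it fails. That depends on an SD the protocol does not give; over the assumed range the figure runs from 6% to 73%.

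**Conclusion.** The point holds as a mismatch between label and rule. The only version of the criterion with a formula tests the limit most favourable to the drug, so a pass shows that a 20% net ALT reduction is not excluded and nothing more. Sections 7.5 and 2.7 claim more than that. Given a residual SD of 30% to 60% of mean ALT (assumed) and equal groups, an inactive drug passes 21% to 73% of the time at n = 70 and 6% to 59% at n = 112, against 2.5% for a rule that required evidence of benefit.

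The synopsis and section 3.3 are loosely worded and should be aligned. If the synopsis were applied as week 24 minus baseline, a true 20% reduction would pass about 2.5% of the time instead of 97.5%. That is the cost of leaving the direction open, not a demonstrated contradiction. The use of b_2 is a definite error in the written specification.

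This should be fixed, but because the criterion is advisory and futility is a legitimate purpose, it is not a defect that the trial must resolve before it can proceed.

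**What to change.** 1. State one sign convention in the synopsis, section 3.3 and section 7.5: baseline minus week 24, obeticholic acid minus placebo, positive meaning benefit.
2. State one rule in all three places, and describe it as an advisory futility guideline under which a 20% net reduction is not excluded.
3. Remove the sufficient-evidence wording from sections 2.7 and 7.5.
4. In section 7.5, take the treatment effect, its standard error and its limit from b_1, the coefficient of x_1, in place of b_2.

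This costs only wording. The section 7.5 rule as intended, and its 97.5% pass rate at a true 20% reduction, are unchanged.

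If the sponsor does mean evidence of benefit, rewording is not enough and the limit tested has to change. That choice, including any floor, is the sponsor's, since the documents give no basis for a particular value. It would have a price: a lower limit above zero would pass a true 20% reduction about 28% of the time at n = 70 and SD 60%, and about 94% at n = 112 and SD 30%.
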